The most common treatment-emergent AEs (TEAEs) across the dose levels that were considered by the Investigator to be related to bempegaldesleukin were fatigue (71.4%), flu-like symptoms (67.9%), pruritus (64.3%), hypotension (57.1%), rash (50.0%), decreased appetite (46.4%), and arthralgia or cough (each 32.1%). Such treatment-related TEAEs as flu-like symptoms, rash, and pruritus were generally mild or moderate in severity, predictable, manageable, and short-lived. These AEs generally occurred approximately 3 to 4 days post-dose, and resolved spontaneously or were mitigated by nonprescription oral or topical treatments. The AEs corresponded to the pharmacokinetics of the active metabolites of bempegaldesleukin, which peaked at approximately 30 hours after dosing. The flu-like symptoms were managed with acetaminophen and nonsteroidal anti-inflammatory drugs (NSAIDs) and the cases of rash/pruritus were either self-limiting or treated with antihistamines.

Hypotension can be effectively mitigated by prophylaxis and hydration guidelines, which were introduced during Study 16-214-02 (PIVOT-02) and are now included in all studies of bempegaldesleukin (see Section 5.5.4).

The lowest bempegaldesleukin dose administered to date, 0.003 mg/kg, was utilized as monotherapy in Study 15-214-01 as part of the dose escalation process and represents the highest dose that could be administered in the current study (Study 20-214-34). Among the four patients treated at that dose there were no Grade 3 or higher instances of hypotension or any occurrence of cytokine release syndrome (see Table 4).

Table 4:	Treatment-emergent Related Adverse Events by Severity Grade
	Following Bempegaldesleukin 0.003 mg/kg Administration (Study
	15-214-01 [EXCEL])

	Bempegaldesleukin 0.003 mg/kg (q3w) (N=4)					
	All C	Cycles	Cycle 1 Only			
Preferred Term	Grade 1-2 n (%)	Grade 3-5 n (%)	Grade 1-2 n (%)	Grade 3-5 n (%)		
Patients with ≥ 1 treatment- related TEAE	4 (100.0)	0	4 (100.0)	0		
Flu-like symptoms ^a	2 (50)	0	1 (25)	0		
Headache	2 (50)	0	1 (25)	0		
Hypotension	2 (50)	0	2 (50)	0		
Pruritus	2 (50)	0	2 (50)	0		
Rash ^b	2 (50)	0	2 (50)	0		
Dizziness	1 (25)	0	1 (25)	0		
Abdominal pain	1 (25)	0	0	0		
Chest discomfort	1 (25)	0	1 (25)	0		
Conjunctivitis	1 (25)	0	1 (25)	0		
Constipation	1 (25)	0	0	0		
Depression	1 (25)	0	1 (25)	0		
Dizziness	1 (25)	0	1 (25)	0		
Dry skin	1 (25)	0	0	0		
Dyspnea	1 (25)	0	0	0		
Hypothyroidism	1 (25)	0	0	0		
Muscular weakness	1 (25)	0	1 (25)	0		

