	Medical Monitor reviews blinded safety and tolerability data for the first 72 hours after study drug administration to determine if Patients 9 and 10 can be randomized. ^a
Patients 9 and 10	Randomize Patients 9 and 10 if Medical Monitor approves.
	After 10 patients receive study drug and a 7-day observation period has elapsed, CRC review to determine if dose escalation or de-escalation from the tested bempegaldesleukin dose level can proceed.

a. If it is not possible to assess the protocol-defined DLT criteria (see Section 5.3.2.1.1), the Medical Monitor will request a review of the safety data by the CRC.

The CRC will decide the following:

- Continued dosing of additional patients after the first 2 sentinel patients in a new cohort are treated and a 72-hour safety review period has elapsed. If it is not possible to assess the protocol-defined DLT criteria (see Section 5.3.2.1.1), the CRC may review unblinded data in accordance with Nektar Therapeutics internal procedures for unblinding.
- If reports of Grade 3 dose-limiting toxicities meet the protocol-defined criteria for a DLT and demonstrate evidence indicating at least a possible relationship to study drug in patients confirmed to have received bempegaldesleukin. If it is not possible to assess the protocol-defined DLT criteria (see Section 5.3.2.1.1), the CRC may review unblinded data in accordance with Nektar Therapeutics internal procedures for unblinding.
- Whether dose escalation or de-escalation from the tested bempegaldesleukin dose level can proceed after 10 patients are treated in a dose cohort and a 7-day observation period has elapsed. The CRC decision will be based on the accumulated, blinded safety and tolerability data, as well as any available pharmacokinetic, pharmacodynamic, and disease measurement data. If it is not possible to assess the protocol-defined DLT criteria (see Section 5.3.2.1.1) for the entire cohort to determine dose escalation, the CRC may review unblinded data in accordance with Nektar Therapeutics internal procedures for unblinding.

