- The RP2D of bempegaldesleukin based on the totality of the blinded, safety, tolerability, pharmacokinetic, pharmacodynamic, and disease measurement data. The RP2D may be determined based on the MTD dose or a dose lower than MTD. The RP2D may also be determined based on the immunologic effects of the study drugs, which could include effects on lymphocyte counts, cytokines, natural killer cells, T-cells, and other serum proteins and immune modulators. If it is not possible to assess the protocol-defined DLT criteria (see Section 5.3.2.1.1) for the entire cohort to determine dose escalation, the CRC may review unblinded data in accordance with Nektar Therapeutics internal procedures for unblinding.
- Whether dose levels other than those shown in Table 8 should be evaluated in consideration of the severity, duration, frequency of toxicities, pharmacokinetics, and/or pharmacodynamics observed at any dose.

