5.3.1 Rules for Dose Finding

The DLT evaluation period will be a minimum of 1 week (7 days) (see Section 5.3.2.1).

Patients will be randomized (1:1 ratio) in groups of at least 10 patients (5 bempegaldesleukin/SOC and 5 placebo/SOC) in each dose cohort unless unacceptable toxicity is observed.

Unblinding patient treatment assignment, if required, for the purpose of dose-limiting toxicity (DLT) adjudication will be performed in accordance with Nektar Therapeutics internal procedures for unblinding and associated documentation.

The definition of a DLT is provided in Section 5.3.2.1. If no DLTs occur in a cohort of at least 5 patients who received bempegaldesleukin, a new cohort of 10 patients may be randomized and treated at the next higher dose level (Table 8). If only 1 of the 5 patients who received bempegaldesleukin in a dose cohort experiences a CRC-confirmed DLT, then the next cohort of 10 patients may be treated at the next higher dose level. If 2 or more patients who received bempegaldesleukin within a cohort experience CRC-confirmed DLTs, then that dose level will be above the MTD (the highest dose tested where no more than 1 of 5 patients who received bempegaldesleukin has experienced a CRC-confirmed DLT). If 10 patients have already been enrolled into a cohort and additional patients have signed the ICF and are undergoing the screening process, they may be enrolled to the cohort with Sponsor approval; however, these patients are not required to be included in the dose escalation or de-escalation decision for that cohort.

Approximately 30 patients will be enrolled.

5.3.2 **Dose-Limiting Toxicities (DLTs)**

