5.4 Study Stopping Criteria

The study will be promptly paused if any of the following are met:

- Death in any patient in which the cause of death is judged to be related to the study drug by the treating Investigator.
- The occurrence in any patient of a life-threatening SAE whose causal relationship to study drug is judged to be related by the treating Investigator.
- If at any dose tested, there are 2 occurrences of treatment-related dose-limiting toxicities defined in Section 5.3.2.1.1 observed in the first 5 or fewer patients dosed with bempegaldesleukin that are adjudicated by the CRC as meeting the criteria of Section 5.3.2.1.1 and are confirmed as related to study drug in patients actually treated with bempegaldesleukin.

If any of the above listed event(s) occur, patient accrual will be suspended pending further review by the CRC and prompt consultation with the US FDA and Institutional Review Boards (IRBs)/ Independent Ethics Committees (IECs).

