5.15 Method of Assigning Patients to Treatment Groups

For each dose cohort, two sentinel patients who meet all screening and eligibility criteria will be assigned randomly in a 1:1 ratio on Day 1 to receive either bempegaldesleukin/SOC or placebo/SOC. Following CRC review of the blinded safety and tolerability data from the first 72 hours after study drug administration for the 2 sentinel patients, the CRC will determine whether additional patients who meet all screening and eligibility criteria will be randomized in a 1:1 ratio within the dose group. Study drug administration will be staggered by 72 hours for every 2 patients (1 bempegaldesleukin/SOC and 1 placebo/SOC) to allow for Medical Monitor review of the blinded safety and tolerability data before the next 2 patients are randomized. As stated in Section 5.3.1, patients who drop out of the study for reasons other than a DLT, before the DLT evaluation period (Days 1 to 7) has elapsed, may be replaced. Therefore, in each dose cohort, a maximum of 10 patients will complete the 7-day DLT evaluation period (ie, a total of 5 patients who receive bempegaldesleukin/SOC and 5 patients who receive placebo/SOC). Study

drug assignment will occur in a blinded fashion in accordance with a computer-generated randomization scheme prepared by Nektar or its designee.

Each patient will be assigned a unique patient number after signing the ICF. Patient numbers will be used on all patients' study information. Patient numbers will not be reassigned.

[figure not shown]
An Interactive Response Technology (IRT) will be employed to manage patient randomization.

Nektar will supply bempegaldesleukin from a central source. Choice of standard of care for an individual patient will depend on what drug products are available at each medical center and the Investigator's choice.

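### Section 5.3.1 lets the committee escalate from a dose that its own two-DLT rule places above the MTD, when the second DLT is in a patient enrolled beyond the planned 10

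*Protocol*

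**What the plan says.** Four statements in Protocol section 5.3.1 bear on this.

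- **Escalation.** The next dose may be opened after no DLTs in at least five patients on bempegaldesleukin, or after a confirmed DLT in only one of the five.
- **Two-or-more rule.** "If 2 or more patients who received bempegaldesleukin within a cohort experience CRC-confirmed DLTs, then that dose level will be above the MTD". It has no denominator and is not limited to the first five on drug.
- **MTD definition**, in parentheses in the same sentence: "the highest dose tested where no more than 1 of 5 patients who received bempegaldesleukin has experienced a CRC-confirmed DLT".
- **Extra patients.** Once 10 are enrolled, patients who have consented and are being screened may still join that cohort if the Sponsor approves. However, "these patients are not required to be included in the dose escalation or de-escalation decision for that cohort".

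Elsewhere, section 5.3 has the CRC decide on escalation "after 10 patients are treated in a dose cohort and a 7-day observation period has elapsed", using accumulated blinded data. The DLT pause in section 5.4 needs two adjudicated DLTs "observed in the first 5 or fewer patients dosed with bempegaldesleukin". Section 5.15 says that "in each dose cohort, a maximum of 10 patients will complete the 7-day DLT evaluation period".

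**The concern.** An extra patient belongs to the cohort, so a confirmed DLT in that patient counts under the two-or-more rule. The last sentence of the paragraph lets the same patient be omitted from the escalation decision, and it makes no exception for a DLT already on record. The protocol can therefore call a dose above the MTD and still allow the study to move to the next higher one.

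The timing makes this more than loose wording. Under section 5.3.2.1.1 a DLT is confirmed only once the patient is known to have received bempegaldesleukin. So when the choice to include or omit is made, the committee may already know both the event and the treatment. Under section 7.16 that committee consists of Sponsor representatives and at least one Principal Investigator. A dose-finding rule is written in advance to remove this kind of choice.

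**Working it through.** **Does another section settle it?**

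- *5.3.1, MTD definition.* It is fixed at one of five and says nothing about a sixth patient on drug.
- *5.3, CRC decision.* It relies on accumulated data, without saying whether extra patients are in or out.
- *5.4.* The DLT pause stops at the first five dosed with bempegaldesleukin. A second DLT in a sixth patient does not trigger it.
- *5.15.* The maximum of 10 is drawn as a consequence of the replacement rule and does not mention extra patients. It also fits poorly with 5.3.1, which sets cohorts of 10 or more.
- *SAP 11.1.* DLTs are summarised by dose level in the Safety Population. The report could show 2 of 6 at a dose from which escalation was based on 1 of 5.

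None of these resolves the conflict.

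**The plan's own figure.** Three cohorts of 10 give 3 × 10 = 30, which matches the approximate total of 30. There is no formal sample size calculation and no stated error rate to reproduce.

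**How often the readings disagree.** The documents give five patients on drug per cohort and a limit of one DLT. They do not give a DLT rate or a number of extra patients. I assume a DLT rate p of 5%, 10% or 20%, one extra patient on drug, and independent patients.

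The readings differ only when exactly one of the first five has a DLT and the extra patient has one too:

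P(disagree) = 5p(1 − p)⁴ × q, where q is the chance that the extra patient's DLT is known at the decision.

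*Full follow-up, q = p:*

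- p = 0.05: 0.2036 × 0.05 = 0.010
- p = 0.10: 0.3281 × 0.10 = 0.033
- p = 0.20: 0.4096 × 0.20 = 0.082

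*Earliest review.* If the 72-hour stagger also applies to extra patients, the first extra pair is dosed 3 days after Patients 9 and 10. That leaves 7 − 3 = 4 days of follow-up at the earliest decision. Assuming a constant daily risk over seven days, q = 1 − (1 − p)^(4/7):

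- p = 0.05: 0.2036 × 0.0289 = 0.006
- p = 0.10: 0.3281 × 0.0584 = 0.019
- p = 0.20: 0.4096 × 0.1197 = 0.049

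Section 5.3.2.1 expects drug-related events mainly on days 1 to 5, so the value at the earliest review probably lies between the two sets.

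**Chance of at most one DLT**, (1 − p)ⁿ + np(1 − p)ⁿ⁻¹, for n patients on drug:

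| p | n = 5 | n = 6 | Difference |
|---|---|---|---|
| 0.05 | 0.977 | 0.967 | 0.010 |
| 0.10 | 0.919 | 0.886 | 0.033 |
| 0.20 | 0.737 | 0.655 | 0.082 |

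The differences match the full-follow-up figures, as they should.

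**The case against.** The sentence about extra patients has an ordinary purpose: to treat people already in screening without holding up escalation. It permits omission and does not order it. Escalation is permissive throughout, and the CRC adjudicates every qualifying event reported as related. Related deaths and related life-threatening SAEs pause the study in any patient. If escalation did proceed, the next cohort would open with two sentinel patients, one on drug, and a 72-hour review, after a two-fold dose step. Extra patients need Sponsor approval, may be allocated to placebo, and may never be enrolled in a study of about 30.

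All of this stands. It limits the consequence but does not supply the missing rule.

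A reader might go further and infer that MTD status itself is undecided at every dose. The text does not support that. The two-or-more rule is mandatory and covers everyone in the cohort, and the permission to omit concerns only the escalation or de-escalation decision. The one-of-five definition is incomplete for a sixth patient, but it does not cancel the operative rule. Nor does the RP2D turn on this count: "The RP2D may be determined based on the MTD dose or a dose lower than MTD", and it rests on the totality of the data.

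A reader might also call the limit in 5.4 an error. It is a coherent early pause, and extending it is a design preference.

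**Conclusion.** The point holds as an inconsistency inside 5.3.1. Escalation from a dose that the same paragraph places above the MTD is permitted, and the choice can be made after the DLT is known.

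Its size is modest. Given one extra patient on drug, the readings disagree in about 0.6% to 3% of such cohorts at DLT rates of 5% to 10%, and in 5% to 8% at 20%. The lower end of each range is four days of follow-up at constant risk, and the upper end is full follow-up. Across all cohorts the chance is lower, because an extra patient must first be enrolled and given drug. Escalation is at stake only below 0.003 mg/kg, which "represents the highest dose that could be administered in the current study".

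The DLT rates are assumptions. The seven cancer patients treated at 0.003 mg/kg (Tables 4 and 5), with no related Grade 3 to 5 events, should not be used to bound them. They cannot inform the DLT criterion for worsening COVID-19. Appendix 5 also lists a 0.003 mg/kg group of three in PIVOT-02 Part 1 with nivolumab, whereas section 2.1.4.2.2 describes its three patients at that dose as receiving monotherapy.

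**What to change.** In Protocol section 5.3.1:

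- State that extra patients need not complete the seven-day period before the escalation decision, but that any CRC-confirmed DLT in a bempegaldesleukin-treated patient of that cohort, if known at the decision, counts toward the two-or-more rule.
- State that a second DLT confirmed later reclassifies the dose as above the MTD and prompts CRC review.
- Reword the MTD definition as the highest dose tested at which no more than one bempegaldesleukin patient in the cohort has had a CRC-confirmed DLT.

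This adds no waiting time. Escalation becomes slightly more conservative when extra patients are enrolled. With one extra on drug and fully followed, the chance of at most one DLT goes from 92% to 89% at a 10% DLT rate, and from 74% to 66% at 20%.

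Extending the 5.4 pause to every bempegaldesleukin patient in the cohort, or capping the number of extra patients, would be compatible with this. Both are optional design choices and are not needed to remove the inconsistency.

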5.3.2.1 Determination of Dose-Limiting Toxicities (DLTs)

The DLT evaluation period will be a minimum of 1 week (7 days) because possible drug-related AEs are most likely to occur 1 to 5 days following bempegaldesleukin treatment based on the following:

- Previous experience with bempegaldesleukin in cancer patients including clinical safety data from 605 patients treated primarily with bempegaldesleukin at higher, oncology dose levels (most often, bempegaldesleukin 0.006 mg/kg) than will be used in this trial (see Section 2.2.4.1).
- The clinical half-life of bempegaldesleukin, which is approximately 20 hours (see Section 2.1.3.1).
- The rate of active species formation from the inactive bempegaldesleukin pro-drug (see Section 2.1.3).
- The chronic nonclinical toxicology studies (see Section 2.2.4.2).

DLTs will be assessed by the CRC during the DLT evaluation period. If DLTs are not observed, dose escalation will be permitted and enrollment of the next dosing cohort may begin. If DLTs are not observed, patients will continue to enroll until no more than 30 patients have been evaluable for safety. Grading of AEs is described in Section 7.3. Patients who drop out of the study for reasons other than a DLT, before the DLT evaluation period has elapsed, may be replaced.

5.3.2.1.1 DLTs Related to Study Drug

AEs related to study drug(s) that will be defined as a DLT include the following:

- Any Grade \geq 3 drug-related AE.
- Any Grade ≥ 3 drug-related laboratory abnormality that is clinically significant per the Investigator.
- Respiratory compromise or other virus-related AE attributed to worsening COVID-19, such as severe hypoxia, cyanosis, or chest pain/pressure.

All AEs that meet DLT criteria must be recorded in the electronic data capture system within approximately 24 hours of awareness.

Each AE reported as related to study drug that meet any of the above definitions will be adjudicated by the CRC. If the event is confirmed to be at least possibly related to study drug, meets any of the above definitions, and is confirmed to have occurred in a patient treated with bempegaldesleukin, the event will be considered to be a DLT.

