2.3 Cohort Review Committee

In addition to routine safety monitoring and pharmacovigilance activities, a Cohort Review Committee (CRC, see Section 7.16) will be formed to review safety and tolerability data throughout the study. Specifically, the CRC will perform the following evaluations:

- Monitor the blinded safety and tolerability data for the first 72 hours after study drug administration from the first two sentinel patients randomized (1 patient receiving bempegaldesleukin/SOC and 1 patient receiving placebo/SOC) and treated to determine if additional patients may be enrolled in the dose cohort. If the CRC determines additional patients may be randomized, 2 patients will be randomized (1 with bempegaldesleukin/SOC and 1 with placebo/SOC), treated with study drug, and observed for 72 hours. For every 2 patients, the Medical Monitor will review the blinded safety and tolerability data for the first 72 hours after study drug administration to determine if the next 2 patients may be randomized. If it is not possible to assess the protocol-defined DLT criteria (see Section 5.3.2.1.1), the Medical Monitor will request a review of the safety data by the CRC. It may be necessary for the CRC to review unblinded data in accordance with Nektar Therapeutics internal procedures for unblinding.
- 2. Adjudicate reports of Grade 3 dose-limiting toxicities to determine if they meet the protocol-defined criteria for a DLT and demonstrate evidence indicating at least a possible relationship to study drug in patients confirmed to have received bempegaldesleukin. If it is not possible to assess the protocol-defined DLT criteria (see Section 5.3.2.1.1), the CRC may review unblinded data in accordance with Nektar Therapeutics internal procedures for unblinding.
- 3. At the conclusion of each dose level cohort, assess the accumulated, blinded safety and tolerability data, as well as any available PK, pharmacodynamic, and disease measurement data, to determine if dose escalation or de-escalation is warranted. If it is not possible to assess the protocol-defined DLT criteria (see Section 5.3.2.1.1) for the entire cohort to determine dose escalation, the CRC may review unblinded data in accordance with Nektar Therapeutics internal procedures for unblinding.
- 4. The CRC will also establish the RP2D.

All instances of patient unblinding will be performed in accordance with Nektar Therapeutics' internal procedures for unblinding and associated documentation.

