7.4 Causality Relationship of AEs

The relationship of each AE to each study drug (bempegaldesleukin or placebo) as applicable will be evaluated by the Investigator using the following definitions:

- Not related: An AE that does not follow a reasonable temporal sequence from administration of study drug(s), and/or that can be reasonably explained by other factors such as the patient's medical history, preexisting medical condition, underlying disease, concurrent illness, or concomitant medications/therapies.
- Related: There is a reasonable possibility that the AE is caused by the study drug(s). A plausible temporal sequence exists between the time of administration of the study drug(s) and the development of the AE, or follows a known pattern to the study drug(s). The AE cannot be reasonably explained by the known characteristics of the patient's clinical state or other concomitant therapies or interventions administered to the patient.

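### Grade 3 or higher events that the investigator codes as not related have no stated route into the CRC-confirmed DLT count, although the CRC's own bar is possible relatedness

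*Protocol*

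**What the plan says.** **Intake to adjudication.** Section 5.3.2.1.1 lists drug-related AEs of Grade 3 or higher and drug-related laboratory abnormalities of Grade 3 or higher that the investigator finds clinically significant, plus a COVID-19 worsening criterion that this point does not rely on. It then says: "Each AE reported as related to study drug that meet any of the above definitions will be adjudicated by the CRC".

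**The CRC's bar.** The same section continues: "If the event is confirmed to be at least possibly related to study drug, meets any of the above definitions", and the patient is confirmed to have received bempegaldesleukin, then the event is a DLT. Section 2.3 likewise has the CRC check that reports "demonstrate evidence indicating at least a possible relationship to study drug in patients confirmed to have received bempegaldesleukin".

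**The investigator's bar.** Section 7.4 offers two categories. Related starts from a reasonable possibility of a causal link, but ends with a further condition: "The AE cannot be reasonably explained by the known characteristics of the patient's clinical state", nor by other therapies. Not related is met, through an and/or, when underlying disease is a reasonable explanation.

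**What the count drives.** Section 5.3.1 places a dose above the MTD on this condition: "If 2 or more patients who received bempegaldesleukin within a cohort experience CRC-confirmed DLTs". With 0 or 1 such DLT among 5 active patients, the next cohort may be treated at the next higher dose. The third pausing rule in Section 5.4 also counts only CRC-adjudicated DLTs, and words their causality as confirmed related.

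**Other wordings of the CRC's task.** Section 5.3 gives the CRC's question as "If reports of Grade 3 dose-limiting toxicities meet the protocol-defined criteria for a DLT", and Section 2.3 also says Grade 3. Section 5.3.2.1.1 says Grade 3 or higher. Section 7.16 refers to AEs already reported as DLTs.

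**The concern.** Two causality tests are applied in sequence, and the one applied first can be the harder to pass. An event that drug and disease could each explain is, in ordinary language, possibly related. That is enough for the CRC, but the last condition of Related and the and/or in Not related both allow the investigator to code it Not related. If that happens, no passage sends it to the CRC for DLT adjudication. The CRC can strike candidates from the list but has no stated means of adding one.

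The ambiguous zone is not empty here. Section 2.1.1.1 lists fever, malaise, headache and muscle pain as symptoms of mild COVID-19. Section 2.1.4.2.6 gives flu-like symptoms, including fever and chills, as the most common AEs of the drug. Section 2.1.4.2.7 accepts that toxicity may differ between cancer and COVID-19 patients, so ambiguous severe events are among those the study exists to examine. With 5 active patients per cohort and a cut at 2, one event left out can change which side of the cut a dose falls on.

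**Working it through.** **Step 1: the path of one event.** Take a Grade 3 or higher AE in a bempegaldesleukin patient during the DLT period, reasonably explained by drug or by COVID-19.

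- Section 7.4, Related: the reasonable-possibility sentence is satisfied; the sentence requiring no other reasonable explanation is not.
- Section 7.4, Not related: satisfied by the underlying-disease limb alone.
- Section 5.3.2.1.1, intake: not reported as related, so not routed to adjudication.
- Section 5.3.2.1.1, CRC bar: would be satisfied if the CRC were asked.
- Sections 2.3, 5.3 and 7.16: each starts from an event already reported as a DLT, so none supplies another route.

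**Step 2: direction.** A counted DLT must pass the investigator's coding and the CRC's bar. The counted events are therefore a subset of those the CRC's bar alone would count. The count is equal or lower, never higher. This needs no numerical assumption.

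**Step 3: illustration of size.** The plan gives no operating characteristics, and Section 9.2 states that no formal sample size calculation was done, so there is no figure to reproduce. Inputs:

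- n = 5 active patients and at most 1 DLT permits escalation (Section 5.3.1).
- p = true per-patient DLT rate by the CRC's bar: assumed.
- s = share of those DLTs also coded related by the investigator: assumed. s = 1 means the intake removes nothing.
- Patients are treated as independent.

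Formula, with q = p × s: P(at most 1 of 5) = (1 − q)^5 + 5q(1 − q)^4.

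Worked case, p = 0.40 and s = 0.75, so q = 0.30: 0.70^5 + 5 × 0.30 × 0.70^4 = 0.168 + 0.360 = 0.528. With s = 1, q = 0.40: 0.078 + 0.259 = 0.337.

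| p (assumed) | s = 1 | s = 0.75 | s = 0.50 |
|---|---|---|---|
| 0.10 | 0.919 | 0.952 | 0.977 |
| 0.20 | 0.737 | 0.835 | 0.919 |
| 0.30 | 0.528 | 0.685 | 0.835 |
| 0.40 | 0.337 | 0.528 | 0.737 |

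Each entry is the chance that the count permits escalation.

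**The case against.** Several objections have force.

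- **Section 7.4 is not plainly strict.** Related opens with a reasonable-possibility test close to the CRC's bar, and a known drug pattern counts in its favour. A reader might infer that most severe events in a COVID-19 patient will be coded Not related. The documents do not support that. Entry requires oxygen saturation above 93% on room air, heart rate below 90 and no shock, so new severe hypotension a few days after dosing is not obviously explained by such a patient's disease. What stands is that the definition points both ways, so coding may differ between investigators.
- **Intake is not worded as exclusive.** Section 5.3.2.1.1 does not say that only related events are adjudicated, and Section 5.3.2.1 says simply that the CRC assesses DLTs. That leaves room for a generous CRC, but nothing instructs it to take up other events.
- **Escalation is not automatic.** The CRC decides on all accumulated blinded safety data with any available PK, pharmacodynamic and disease data, the Medical Monitor reviews successive pairs after the sentinels, and the CRC may unblind if the DLT criteria cannot be assessed. A reader might take the table as the chance that a toxic dose is cleared. It is not. This objection stands in full, but it does not alter the count, the MTD definition or the third pausing rule.
- **The assumed rates may be high.** Tables 4 and 5 show no related Grade 3 to 5 events in 4 + 3 = 7 cancer patients at 0.003 mg/kg. At p = 0.10 the shift is only 3 to 6 points. Seven patients with another disease settle little, but the caution is fair.
- **Grade 3 against Grade 3 or higher** matters little in practice. Section 5.3.2.1.1 is the controlling definition, and deaths and life-threatening SAEs that the investigator judges related pause the study separately.

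**Conclusion.** The point holds for the formal DLT count. As written, a Grade 3 or higher event that drug or disease could explain may be coded Not related and then has no stated route to CRC confirmation, although it would meet the CRC's own bar. The direction follows from the text: relative to that bar, the count is equal or lower. The size does not follow, because the documents give neither the true rate nor the share coded related. Over assumed rates of 20% to 40%, losing a quarter of such events raises the chance that the count permits escalation by about 10 to 19 points, and losing half raises it by about 18 to 40 points. The effect is on the count, the MTD definition and the third pausing rule, not on every escalation decision.

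**What to change.** In Section 5.3.2.1.1, have the CRC adjudicate, whatever the investigator's causality, every AE of Grade 3 or higher in the DLT period, and every laboratory abnormality of Grade 3 or higher that meets the section's existing clinical-significance condition. Use the CRC's existing possible-relatedness bar. Leave the grade thresholds and the escalation cut as they are, and keep the investigator's causality for SAE reporting.

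Reconcile with that section the Grade 3 wording in Sections 2.3 and 5.3, the confirmed-as-related wording in Section 5.4, and the reference in Section 7.16 to AEs reported as DLTs.

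The cost is protocol wording and a few more events for an existing committee, in cohorts of about 10 patients. There is also a statistical cost: the count may rise, because some disease events may be accepted as possibly related and the rule makes no comparison with placebo.
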